#### Overview of Cost/Health Care Utilization Data.

Costs to be collected for the trial	From electric medical record	From patient report
Antidepressant cost, therapy cost, other mental health visits	Х	X
Depression-free days		X
Primary care visits, ED/urgent care, other medical visits, diagnostic services, inpatient services other outpatient services	Х	
Days able to work/impact on work and leisure productivity		X

We will generate cost data using a combination of EMR extraction and patient surveys as detailed in the table above. We will calculate the cost of all possible depression care used (antidepressant cost and therapy cost. We will also collect data on all non-study delivery of depression treatment utilization from patient report and EMR. To derive other healthcare costs, we will use the EMR to collect data on all episodes of non-depression related healthcare utilization during the 18-month trial period: outpatient visits, ED/urgent care, as well as all in-patient care and any diagnostic tests or services. Average Medicare reimbursement rates according to diagnosis-related groups will be applied to inpatient visits to estimate hospitalization costs, and the Medicare fee schedule will be applied to outpatient and ED resource use according to current

procedural terminology codes. Finally, to calculate costs and potential cost-offsets from a societal perspective, we will collect participant report data on time lost from work. Lost productivity is believed by many experts to be assessed in our measure of health-related QoL instrument, the SF12. However, a sensitivity analysis will be conducted to test this assumption.

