#### **Hypothesis 2:**

Those randomized to AHA's Depression Screen, Notify & Treat intervention group will have a favorable incremental cost-effectiveness ratio when compared to No Depression Screen control group and also when compared to the Depression Screen & Notify control group.

For this hypothesis, we will judge the cost effectiveness of AHA Screen, Notify & Treat group compared to the Screen & Notify group, then we will compare the Screen & Notify group to the No Screen group on the basis of incremental cost-effectiveness ratios. The base case analysis will adopt a societal perspective with respect to costs and health benefits. Costs will include all healthcare costs and lost productivity cost related to use of website/staff time for depression screening, and the cost of all possible depression care used (antidepressant cost and therapy cost, including the cost for telephone/webcam use). Costs will be denominated in 2012 dollars and discounted at an annual rate of 3% as per the Panel on Cost-Effectiveness in Health and Medicine. For health benefits, we will convert SF-12 scores to QALYs, using the four (prerandomization, 6, 12, & 18 month) measured values. Incremental cost-effectiveness analyses for comparison of treatment groups will be calculated sequentially using the ratio of the difference in average cost per participant divided by the difference in average QALY gained.

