The other prespecified secondary outcome will be Health Care Costs and Lost Productivity. 1 At baseline, 6-months, 12-months, and 18-months, patients will report measures of economic productivity, including employment status, occupation, hours spent at work, and time lost from work for health-related reasons.11 At 6-months, 12-months, and 18-months, patients will also report healthcare utilization since their last intake assessment, including emergency department (ED) visits, hospitalizations (location, admission and discharge dates), psychiatric medication use, name and dose, ambulatory care visits with mental health specialists, cardiologists, as well as PCPs and finally hospitalizations for cardiovascular events. Patient self-reports of healthcare utilization will be supplemented by review of the EMR and claims systems to collect data on healthcare utilization during the 18-month trial period. Average Medicare reimbursement rates according to diagnosis-related groups will be applied to inpatient visits to estimate hospitalization costs, and the Medicare physician fee schedule will be applied to outpatient and ED resource use according to current procedural terminology codes. Costs of study depression treatment will also be incorporated into estimates of healthcare utilization costs for those assigned to the Screen, Notify, and Treat group who agree to depression treatment by study personnel. To estimate economic costs from a societal perspective, changes in productivity and time spent traveling to appointments will also be accounted for. Costs will be standardized across years using the U.S. Consumer Price Index and presented in U.S. dollars.12

-

¹Cost of health care utilization was erroneously listed as a co-primary outcome on the initial clinicaltrials.gov entry. This error was corrected in clinicaltrials.gov on October 25, 2017, prior to completion of data collection or any interim data analyses. As can be seen in the planned statistical analyses, the sample size for the study was driven entirely by the change in QALYs outcome. Cost-effectiveness analyses, in contrast, were never intended to be listed as a co-primary outcome as they were not guided by economic hypotheses involving statistical tests and sample size calculations for incremental cost-effectiveness ratios were never attempted.

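### SAP 8 names the physician fee schedule for emergency and outpatient care and DRG rates for admissions, which leaves hospital facility payments and inpatient professional fees without a stated price

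*SAP*

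**What the plan says.** SAP 8 (Health Care Costs and Lost Productivity) gives one price source per setting. For admissions: "Average Medicare reimbursement rates according to diagnosis-related groups will be applied to inpatient visits to estimate hospitalization costs". For everything else: "the Medicare physician fee schedule will be applied to outpatient and ED resource use according to current procedural terminology codes".

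The protocol (Overview of Cost/Health Care Utilization Data) has the same pair of rules, but its second one reads "the Medicare fee schedule will be applied to outpatient and ED resource use", without the word *physician*. The SAP does not explain the narrower wording.

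On scope, the protocol's base case under Hypothesis 2 takes a societal perspective and states "Costs will include all healthcare costs".

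On data sources, the SAP lists patient-reported items such as "hospitalizations (location, admission and discharge dates), psychiatric medication use, name and dose", and then adds: "Patient self-reports of healthcare utilization will be supplemented by review of the EMR and claims systems". The protocol takes emergency, inpatient and general outpatient use from the medical record.

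**The concern.** A single encounter in a hospital usually generates two payments, one to the hospital and one to the clinicians. That is general knowledge of Medicare billing and is not stated in either document. If it is right, each rule in SAP 8 covers one of the two. The physician schedule would price the clinician's part of an emergency or hospital-outpatient visit but not the hospital's. DRG rates would price the hospital's part of an admission but not the clinicians'.

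Two results are at stake. Health care cost per arm is a prespecified secondary outcome and would be reported too low. The ICER takes the between-arm cost difference as its numerator, so a real difference in acute-care use, whether a saving or an excess, would be counted at only part of its value. In this post-ACS population, emergency visits and admissions are where a cost offset from depression care would be looked for.

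**Working it through.** **Step 1. Set the rules side by side.** The last column rests on the general understanding of Medicare payment described above; the other columns come from the documents.

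| Care | Protocol price source | SAP 8 price source | Component with no named price under SAP 8, read literally |
|---|---|---|---|
| Emergency, hospital outpatient | Medicare fee schedule, by procedure code | Medicare *physician* fee schedule, by procedure code | Facility payment |
| Admission | Medicare rates by DRG | Medicare rates by DRG | Professional services during the stay |

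The protocol's broader term leaves room for a facility price in the first row, and the SAP's term does not. In the second row neither document names a professional fee.

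**Step 2. Effect on the two results.** For one event type, let p be the part that is priced, f the part that is not, and n_T and n_C the mean events per participant in the two arms compared.

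- Mean cost is understated by n_T × f in one arm and n_C × f in the other.
- The true cost difference is (n_T − n_C)(p + f); the computed one is (n_T − n_C)p.
- The omitted incremental cost is (n_T − n_C)f. It is zero when n_T = n_C.
- ICER shift = (n_T − n_C)f / ΔQALY.

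**Step 3. The denominator.** The documents state no cost, unit price, event rate or ICER, so there is no plan figure for cost to reproduce. The planned QALY difference can be reproduced from Sample Size: 0.21 × 0.2 + 0.055 × 0.8 = 0.086, and 0.086 − 0.055 = 0.031. This applies to Screen, Notify & Treat against either control. The planning assumptions give the two controls the same gain (0.055 − 0.055 = 0), so no comparable figure exists for the planned ICER of Screen & Notify against No Screen.

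**Step 4. Unit shift.** $10 / 0.031 = $323 per QALY; $100 / 0.031 = $3,226 per QALY. With an observed difference of 0.010 instead, $10 would move the ICER by $1,000 per QALY.

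**Step 5. Illustration.** Every price and event difference in this table is assumed.

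| Event | Arm difference per participant | Omitted per event | Omitted per participant | ICER shift at 0.031 |
|---|---|---|---|---|
| Emergency visit | 0 | $500–2,000 | $0 | $0 |
| Emergency visit | 0.01 | $500–2,000 | $5–20 | $161–645 |
| Emergency visit | 0.05 | $500–2,000 | $25–100 | $806–3,226 |
| Emergency visit | 0.10 | $500–2,000 | $50–200 | $1,613–6,452 |
| Admission | 0.03 | $1,500–3,000 | $45–90 | $1,452–2,903 |

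The direction follows the sign of the arm difference. If the intervention arm has fewer events, a saving is lost and the ICER comes out too high; if it has more, the ICER comes out too low.

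**The case against.** The strongest reply is that the split between facility and professional payment is nowhere in the documents, and that SAP 8 does not say its price sources are exclusive. An analyst guided by the base case would add what is missing. Part of this stands: the omission follows from a literal reading plus general billing knowledge, and it is not a documented exclusion. But SAP 8 is where the pricing rule is fixed, it chose a narrower term than the protocol, and it names nothing for the other component. An analyst who followed it as written would leave that component out.

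The base-case sentence can also be read narrowly, because it runs on to screening-related time. The protocol's cost-data section argues against that reading: "we will use the EMR to collect data on all episodes of non-depression related healthcare utilization during the 18-month trial period".

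The protocol's Sensitivity Analysis includes actual costs from the health systems and charge-to-cost ratios. That is a real mitigation, but it is not the base case and SAP 8 does not repeat it. It is also true that costs are secondary, that no test or power calculation attaches to the ICER, and that equal omissions cancel.

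A reader might go further and infer that self-reported events, which the SAP lists without billing codes, are dropped, so that large parts of acute-care cost disappear. The documents do not support this. Self-report is supplemented by record and claims review, and the protocol takes acute care from the record, so the gap is confined to events seen only in self-report. On those the plan is silent; it does not say that they are excluded.

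A reader might also infer that outside mental-health care in notified controls goes unpriced and inflates the cost increment of Screen, Notify & Treat over Screen & Notify. That is conjecture. The protocol plans to collect non-study depression care from both sources and to cost all depression care used. Participants in the treatment arm may decline study therapy and seek care elsewhere too. No document gives an uncoded share by arm.

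**Conclusion.** The concern holds in a limited form. SAP 8 narrows the protocol's fee-schedule wording and names one price source per setting. Taken literally, that leaves the facility part of emergency and hospital-outpatient care and the professional part of inpatient care without a price, against a base case meant to cover all healthcare costs.

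Mean cost per arm would then be understated. The ICER is affected only to the extent that this use differs between arms. The size cannot be determined from the documents; the firm statement is about $323 per QALY for each $10 per participant of omitted incremental cost at the planned 0.031. The conclusion assumes the usual division of Medicare payments and a literal application of SAP 8. The primary QALY analysis is not touched.

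**What to change.** In SAP 8, price each emergency and hospital-outpatient visit as the professional fee plus the Medicare hospital-outpatient facility payment, and each admission as the DRG payment plus professional fees, with a stated rule for admissions whose professional codes are absent. Apply the same rules in all arms, and make the fee-schedule wording agree with the protocol's cost-data section.

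As a minor clarification, state how self-reported events are handled: match them to record and claims data first, and give a mean cost for the event type only to those with no match. Without the matching step, an event found in both sources would be costed twice.

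The cost is SAP wording and a larger unit-cost table built from public Medicare rates. No new patient data are needed. Reported mean costs will be higher, and the average applied to unmatched events is approximate.
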